6. STATISTICAL CONSIDERATIONS

The primary outcome for COSMOS-Mind is a composite measure of cognitive function that combines individual assessments of global cognitive function (TICSm), memory (SR), and executive function (OTMT, Verbal Fluency, NST, DOT). The composite provides a quantifiable measure of cognitive function across multiple domains and greater statistical power than individual measures even if the intervention effect varies moderately from one individual measure to another. It consolidates type 1 error into a single outcome. Secondary analyses, described below, will examine intervention effects on the constituent measures of the composite score.

The primary hypothesis is that random assignment to high potency cocoa flavanol extract compared to placebo will result in a mean difference over time in the global cognitive composite score. This hypothesis will be tested using 2-tailed type 1 error of 0.05. Inference will be based on the marginal effect estimated from a factorial study design, and a generalized linear model¹⁰¹ with the dependent variable consisting of all measured annual changes from baseline across years of follow-up on every participant, regardless of adherence (i.e. intent-to-treat). Data from the individual tests will be combined using a multivariate analysis of covariance (MANOVA) model within this framework with adjustment for sex, education, and age. In this model, all observed data can be included without special procedures for missing data, provided they are missing at random. The estimated differences will be combined using the ordinary least squares global test statistic.^{102,103} This statistic is the sum of the estimated differences of the individual tests divided by their standard errors, which produces a test statistic that is approximately normal with mean zero under the null hypothesis of no difference. Its standard error will be computed from the estimated correlation matrix of the treatment group differences. Cocoa flavanol effects will be examined by comparing cognitive response to active cocoa extract vs. its placebo, regardless of assignment to active MTV or its placebo.

Secondary and tertiary aims. COSMOS-Mind will assess the relative effects of assignment to MTV using parallel analyses to those described above. The study will also assess whether effects of the two treatments interact on the primary outcome, adding a term to the model used in the primary hypothesis. If so, results from the primary marginal comparisons will be qualified. Individual cognitive test scores will be analyzed – paralleling the strategy used to test the primary hypothesis – in supporting analyses. The randomization effects on tertiary outcomes including cognitive complaints, sleep quality, and depressive symptoms will be assessed similarly to the intervention models used in the primary and secondary aims, and further tests will determine whether the treatments interact with respect to tertiary outcomes. Linear contrasts will be used to estimate treatment effects at 3 years. Tests of interactions will also assess the potential moderating effect of treatments among subgroups formed by age (<70 or ≥70 years old), sex, BMI (<25, 25-29, ≥30 kg/m²), baseline cognitive function (median split on TICSm), cognitive complaints (median split on CCI), depressive symptoms (median split on GDS-SF), hypertension, and diabetes; additionally, the preceding variables will also be assessed as continuous moderators of the intervention effects. The distribution of follow-up times to MCI and dementia will be assessed with proportional hazards regression. COSMOS-Mind will incorporate CVD and cancer events (from the parent trial) as change-points in the primary analyses to assess their impact on post-event cognitive trajectories. When needed, transformations (e.g. Box-Cox, rank, probit) will be used to improve the symmetry of residual distributions.

Interim Testing

No interim monitoring of treatment effects on cognitive outcomes is planned. COSMOS-Mind investigators will remain masked to treatment assignment until the parent trial is completed. Routine reports will assess retention, data completeness and quality, and cognitive trajectories over time. These reports will be sent to the COSMOS Coordinating Center for inclusion in DSMB reports.

Statistical Power

Longitudinal sequences of cognitive test scores from the WHIMS-ECHO study (N=2,878; 1-6 years of annual telephone assessments) were used to calculate the longitudinal covariance of measures in a simulation analysis. Loss-to-follow-up was set to accumulate at 5% per year, as per rates observed in WHIMS.¹⁰⁴ Based

on previous studies,^{20,55} the intervention effect appears quickly and is sustained over time. Calculations are based on 2-sided tests with type 1 error set to 0.05 and 90% power for the primary outcome of a composite across all cognitive tests. Based on these and other projections, the 2500-person sample in COSMOS-Mind will provide >90% power to detect a sustained effect size of 0.10 SD and a waning effect size that initially is 0.15 SD; it also provides some leeway should the assumptions made above be not fully realized. Limiting follow-up to 3 years allows a more extended enrollment and analysis period, and reduces the number of assessments.

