4. STUDY POPULATION

Inclusion and Exclusion Criteria

COSMOS-Mind will **include** 2500 participants from the parent trial who are at least 65 years of age, with approximately equal distribution of women and men.

The study will **exclude** participants with insulin-dependent diabetes. Insulin therapy, often associated with chronic hyperinsulinemia, can worsen cognition⁷⁴ and therefore potentially mask beneficial effects of the cocoa flavanols. COSMOS participants co-enrolled in the WHI Memory Study (WHIMS) will be excluded given their prior exposure to COSMOS-Mind cognitive tests. Also, participants who are unable to complete the baseline cognitive assessment will not be permitted to continue in the study. Adults with dementia will likely self-select out of enrollment in COSMOS-Mind, or be excluded given the demands of the placebo run-in period required for COSMOS. For the few with mild dementia who may enroll in COSMOS-Mind, randomization will ensure equal distribution by treatment assignment. Pre-enrollment cognitive assessments to identify dementia are not feasible for this large simple trial.

Recruitment and Consenting

Eligible COSMOS participants will be approached for enrollment in COSMOS-Mind and a second cognitive ancillary study (“COSMOS-Web”: involves a brief online computer assessment) using a single approach letter and recruitment flyer during the placebo run-in phase of the COSMOS trial. These materials provide information about COSMOS-Mind, expectations of participants, what is provided to participants, and how to enroll in the sub-study. Participants can choose to participate in one, both, or neither sub-study and will let the BWH Coordinating Center know of their decision by completing and returning a provided form. Consent to participate will be implied when participants indicate their willingness to participate in COSMOS-Mind on this form or by informing the COSMOS team by telephone or email. Implied consent will be used given the low participant burden and low risk associated with study participation as per Wake Forest School of Medicine IRB accepted practices.

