 - Create z-score by dividing the difference between individual scores and the raw cohort-wide baseline mean by the raw cohort-wide standard deviation

EF4. Attention/Working Memory 1

- Test: Number Span Forward and Backward
- Variables: dst_forwardtot; dst_backwardTot
- Approach
 - Sum digit forward and backwards scores (requires both to be non-missing)
 - Create z-scores by dividing the difference between individual scores and the raw cohort-wide baseline mean by the raw cohort-wide standard deviation

Composite Scores

General Cognitive Function

- Equal to GC1

Global Episodic Memory

- Average MEM1-MEM3, ignoring any missing data
- Create z-score by dividing the difference between individual scores and the raw cohort-wide baseline mean by the raw cohort-wide baseline standard deviation

Global Executive Function

- Average EF1-EF4, ignoring any missing data
- Create z-score by dividing the difference between individual scores and the raw cohort-wide baseline mean by the raw cohort-wide baseline standard deviation

Global Cognitive Composite

- Average z-scores from the following individual tests (note that this differs from averaging the three domain-specific z-scores and includes TICSm (Long) and Oral Trails A, which don't contribute to any of these):
 - TICSm total score
 - TICSm-Long to assess delayed memory
 - Story recall (immediate)
 - Story recall (delayed)

- Oral trails A (based on log transformation)
- Oral trails B (based on log transformation)
- Verbal fluency
- Category fluency
- Number span test (total of forward and backward)
- Create z-score by dividing the difference between individual scores and the raw cohort-wide baseline mean by the raw cohort-wide standard deviation

In the primary analyses, to follow intention-to-treat and use all available data to compare changes from baseline, we will include all cognitive assessments (baseline through Year 3) as dependent variables in general linear models (including data from participants with incomplete follow-up) and use linear contrasts to compare the average changes from baseline across follow-up between intervention groups: the difference between the average means at years 1, 2, and 3 and the baseline mean.

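### The primary change-from-baseline analysis states neither a baseline-score covariate nor an equal-baseline constraint, and so gives up precision that the collected baseline scores could supply

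*Protocol*

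**What the plan says.** Protocol section 6 defines the primary model through a "dependent variable consisting of all measured annual changes from baseline across years of follow-up on every participant", "with adjustment for sex, education, and age". The baseline score is not among the covariates. Baseline TICSm appears in that section only as a subgroup factor and continuous moderator. The individual tests are then combined into the "sum of the estimated differences of the individual tests divided by their standard errors".

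The SAP's closing paragraph on the primary analyses sets the model up differently. It will "include all cognitive assessments (baseline through Year 3) as dependent variables in general linear models", and the group comparison is of "the difference between the average means at years 1, 2, and 3 and the baseline mean". It names no covariates and does not say whether baseline means are free to differ by arm or held in common.

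On timing, Protocol section 4 places the approach to participants "during the placebo run-in phase of the COSMOS trial". Neither document says that the baseline telephone assessment precedes randomisation or the first dose of study product.

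**The concern.** A change score subtracts the whole baseline value, which amounts to a baseline coefficient of 1. The SAP contrast with a separate baseline mean per arm does the same when data are complete. When the between-visit correlation is below 1, the best coefficient is also below 1, and subtracting the full baseline adds measurement noise to the treatment comparison. If baseline is measured before randomisation, the true arm means at baseline are equal. A model that uses this fact estimates the same effect with a smaller standard error.

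The choice reaches beyond the primary test, because section 6 plans parallel analyses for the multivitamin comparison and the individual tests. The gain is larger for any outcome that correlates less between visits.

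Timing decides which remedy is valid. If some baseline calls follow the first dose, equal baseline means need justification. The planned change score would then also subtract part of any early effect, and the power section assumes that "the intervention effect appears quickly and is sustained over time".

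**Working it through.** **Inputs from the documents.** N = 2500; two-sided alpha 0.05 ("This hypothesis will be tested using 2-tailed type 1 error of 0.05"); 90% power; sustained effect 0.10 SD; loss accumulating at 5% per year; the SAP contrast, mean of years 1 to 3 minus baseline.

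**Assumptions.** 1250 v 1250 for the marginal cocoa comparison (no ratio is stated); unit baseline SD; equal correlation ρ between all visits; 100/95/90/85% observed at baseline and years 1, 2 and 3. Section 6 says the longitudinal covariance came from an outside cohort but prints no value, so ρ is varied.

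**Complete data.** Variance per person:

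- Change contrast: (4/3)(1 − ρ).
- Baseline-adjusted or common-baseline contrast: (1 + 2ρ)/3 − ρ² = (1 − ρ)(1 + 3ρ)/3.
- Ratio: (1 + 3ρ)/4, a reduction of 0.75(1 − ρ).

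At ρ = 0.6 the variances are 0.533 and 0.373, a ratio of 0.70. The standard errors, √(2 × variance/1250), are 0.0292 and 0.0244.

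**The plan's own figure.** Power above 90% at 0.10 SD cannot be reproduced without ρ. It requires SE ≤ 0.10/(1.960 + 1.282) = 0.0309. The change contrast reaches this when ρ is at least about 0.55 with no loss, or 0.58 with the 5% yearly loss. The statement is therefore attainable.

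**With loss.** Generalised least squares for four visits, baseline means free by arm v held in common; detectable effect = 3.2415 × SE:

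| ρ | SE free | SE common | Variance cut | Detectable at 90% power (SD) | Power at 0.10 SD |
|---|---|---|---|---|---|
| 0.5 | 0.0336 | 0.0270 | 35.5% | 0.109 → 0.087 | 84.6% → 96.0% |
| 0.6 | 0.0301 | 0.0255 | 28.3% | 0.098 → 0.083 | 91.4% → 97.5% |
| 0.7 | 0.0261 | 0.0232 | 21.1% | 0.085 → 0.075 | 96.9% → 99.1% |
| 0.8 | 0.0214 | 0.0198 | 14.0% | 0.069 → 0.064 | 99.7% → 99.9% |
| 0.85 | 0.0185 | 0.0175 | 10.5% | 0.060 → 0.057 | both >99.9% |
| 0.9 | 0.0151 | 0.0146 | 7.0% | 0.049 → 0.047 | both >99.9% |

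For ρ of 0.6 to 0.8, the precision the planned contrast gets from 2500 people would need about 2500 × 0.717 = 1793 to 2500 × 0.860 = 2150.

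**Sensitivity.**

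- If the correlation decays by a factor of 0.95 or 0.90 per extra year of lag, the cut becomes 30% or 31% at one-year ρ = 0.6, and 16% or 18% at 0.8.
- If sex, education and age explain 10% to 30% of the stable variance, the variance ratio at ρ = 0.6 is 0.69 to 0.59. Time-constant covariate effects cancel from a change score, so listing these covariates does not recover the loss.

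**The Protocol's sum statistic.** Assume six tests, single-test ρ = 0.6, same-visit between-test correlation 0.3, cross-visit between-test correlation c, and no loss. The summed score has between-visit correlation ρ_S = (6 × 0.6 + 30c)/(6 + 30 × 0.3) = (3.6 + 30c)/15. Its variance is compared with (4/3)(1 − ρ_S) for change scores:

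- All baselines jointly: ratio (1 + 3ρ_S)/4.
- Each test on its own baseline only (coefficient 0.6): variance (1 + 2ρ_S)/3 − 1.2ρ_S + 0.36.

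| c | ρ_S | Ratio, own baseline | Ratio, all baselines |
|---|---|---|---|
| 0.30 | 0.84 | 0.2453/0.2133 = 1.15 | 0.88 |
| 0.25 | 0.74 | 0.2987/0.3467 = 0.86 | 0.81 |
| 0.20 | 0.64 | 0.3520/0.4800 = 0.73 | 0.73 |

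Adding the 5% yearly loss moves these ratios by about 0.02 at most. Joint adjustment helps in every case shown; test-by-test adjustment can do worse than the change score.

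**The case against.** Five points can be made for the plan.

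- **The SAP is silent, not wrong.** Baseline is already in its response vector, and the stated contrast would read the same with free or common baseline means. This stands: only the Protocol shows the omission directly, and against the SAP the claim is that the model is under-specified.
- **ρ = 0.5 sits awkwardly with the stated power.** If the power simulation used this contrast in baseline SD units, ρ must be at least about 0.58. This also stands as a matter of emphasis. The simulated model is not printed, so 0.5 is not excluded, but the 36% figure should not lead.
- **A composite is steadier than its parts.** With single-test ρ = 0.6 and same-visit correlation 0.3, a nine-score average has ρ = (9 × 0.6 + 72c)/(9 + 72 × 0.3) = 0.65, 0.76 or 0.88 for c = 0.20, 0.25 or 0.30. The cuts are then about 25%, 17% or 8%, and power at 0.10 SD is already 94% or more. This limits the gain for the primary test; individual tests at ρ = 0.6 would still gain about 28%.
- **The remedy is not automatic.** Test-by-test adjustment of the sum statistic can raise the variance, and the equal-effect assumption behind those figures is a simplification. This is a reason to specify joint adjustment, not to leave baseline unused.
- **No passage puts a baseline call after the first dose.** Recruitment during run-in, and the reliance in section 4 on randomisation to balance mild dementia, lean towards a baseline before randomisation. They do not establish it; one sentence would.

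None of this removes the gain, which exists at any ρ below 1.

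**Conclusion.** The concern holds as an efficiency point. Neither document states a baseline covariate or an equal-baseline constraint. If baseline precedes randomisation, the planned contrast is unbiased, no type 1 error problem arises, and the power statement can be true as it stands.

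What is lost depends on a correlation the documents do not give. For the SAP composite, under equal correlation, 1:1 allocation and 5% yearly loss, it is about 14% to 28% of the variance for ρ from 0.8 to 0.6, and about 7% at 0.9. For the Protocol's sum statistic, joint use of all baselines saves roughly 12% to 27% without loss to follow-up under the correlations assumed above. The change should be made, but the trial's validity does not depend on it.

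**What to change.** 1. State whether the baseline assessment precedes randomisation, or at least the first dose, for every participant.
2. State which primary model governs, the Protocol's or the SAP's, and how baseline enters it.
3. If baseline precedes randomisation or first dose, choose one of two forms. Either keep the SAP's baseline-through-Year-3 response vector and constrain baseline means to be equal across the randomised arms, or model years 1 to 3 with the baseline score and its interaction with year as covariates. Keep sex, education and age in both. The primary contrast is the arm difference averaged over years 1 to 3.
4. If the sum statistic is kept, constrain or condition on the baseline scores of all component tests jointly, not test by test.
5. Use the same model for the multivitamin, domain and single-test analyses.
6. If some baseline calls follow the first dose, justify the equal-baseline assumption before using it, and acknowledge that the change score may subtract part of an early effect.

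The cost is one sentence on timing, one on the role of baseline, and a revised model statement. No new data are needed. The change is nearly free only if baseline precedes randomisation or first dose. It should be fixed before unblinding, since the choice can alter the primary p-value.

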2. OBJECTIVES

COSMOS-Mind is an ancillary cognitive study to the large randomized double-blind, placebo-controlled COSMOS trial, coordinated through Brigham and Women's Hospital (BWH). The parent trial will test whether high-potency cocoa extract supplement administered alone or in combination with a standard multivitamin reduce risks of CVD and cancer in older adults. COSMOS-Mind will test whether 3 years of treatment with these supplements improves cognitive function and reduces risk of cognitive impairment, including AD and other forms of dementia.

Primary Aim

- Test whether random assignment to daily cocoa extract (capsule containing 750 mg/d flavanols, including 75 mg (-)-epicatechin, and 90 mg theobromine), compared to placebo, has favorable effects on a composite measure of cognitive function, over 3 years of follow-up in men and women who are 65 years and older

Secondary Aims

- Examine the effects of MTV use over 3 years of follow-up, relative to placebo, on a composite measure of cognitive function
- Assess treatment effects on incident MCI, and AD and other related dementias
- Compare intervention effects on cognitive domains of executive function and episodic memory

Tertiary Aims

- Examine consistency of treatment response for subgroups defined by age, sex, body mass index, baseline cognitive status, CVD, and type 2 diabetes
- Examine treatment effects on measures of sleep quality, depressive symptoms, and subjective memory concerns
- Share COSMOS-Mind data with the parent trial and its ancillary studies to expand its scientific impact

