Geriatric Depression Scale-Short Form (GDS-SF) measures depressive symptom severity,^{95,96} which is known to affect cognitive function. This 15-item (Yes/No) questionnaire can be administered orally, and has excellent psychometric properties and normative data.^{97,98} Participants who score >8 on this scale or whose general responses to examiners’ questions suggest significant emotional distress will also receive the supplemental Emotional Distress Test, which includes standardized questions about depressive severity and suicidal ideation. If a participant indicates any suicidal inclination, a study clinician experienced in the assessment and treatment of geriatric psychiatric disorders ([name]) will be informed, and will contact the participant to evaluate risk and make recommendations for follow-up.

Women’s Health Initiative Insomnia Rating Scale measures sleep disturbance and insomnia, which are known to impact cognitive function. This 5-item self-report questionnaire has excellent reliability and construct validity, and is sensitive to change over time.^{99,100}

Adjudication of Cognitive Status to Identify MCI, AD and Other Dementias

COSMOS-Mind will use the same procedures for ascertaining MCI and probable dementia (including AD) that were developed for WHIMS. All participants will be asked to identify a reliable informant at the time of the first telephone contact who could provide information about the participant’s cognitive and functional status. After each telephone cognitive assessment, suspected cases of cognitive impairment will be identified when TICSm<31, or, in follow-up Years 1-3 when the TICSm score drops by 0.5 of a standard deviation relative to age-appropriate normative data. For these participants, a trained interviewer will contact their informant to conduct a structured interview to complete the Dementia Questionnaire (DQ). This interview includes questions about current cognitive and behavioral functioning, and medical events and conditions that could impact cognition (e.g., stroke, psychiatric disorders).

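### The hazards model for MCI and dementia names no covariates; adjusting for age, sex, education and baseline TICSm would recover some power at almost no cost

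*Protocol*

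**What the plan says.** Protocol section 2 lists this among the secondary aims: "Assess treatment effects on incident MCI, and AD and other related dementias". The analysis is given in section 6, under secondary and tertiary aims: "The distribution of follow-up times to MCI and dementia will be assessed with proportional hazards regression". Nothing is said about covariates, in either direction.

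The covariates of the primary analysis appear earlier in section 6. The individual tests are combined in a multivariate linear model "within this framework with adjustment for sex, education, and age". The same section says where that approach carries over. For the multivitamin: "COSMOS-Mind will assess the relative effects of assignment to MTV using parallel analyses to those described above". For the tertiary outcomes, the effects "will be assessed similarly to the intervention models used in the primary and secondary aims". The individual test scores are also said to parallel the primary strategy. The hazards sentence has no such link.

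The SAP defines the cognitive scores and the linear model for change. It contains no time-to-event section.

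Baseline TICSm is named in section 6 only as a subgroup and moderator variable. It is not an adjustment covariate in the primary model or in any of the analyses modelled on it.

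**The concern.** In a proportional hazards model, leaving out a baseline variable that strongly predicts the event moves a non-null hazard ratio toward 1 and leaves its standard error almost unchanged. The test statistic shrinks and power falls, even though randomization keeps the comparison fair.

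Age and baseline cognition are plausible predictors here. Case finding runs through the TICSm: section 5 says "suspected cases of cognitive impairment will be identified when TICSm<31", so someone who enters just above that threshold needs little decline to be referred.

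At stake is the efficiency of the only diagnosed clinical outcome in the aims. Section 6 gives a power figure for the cognitive composite but none for MCI or dementia. If the gap were filled by analogy with the primary model, age, sex and education would enter but baseline cognition still would not.

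**Working it through.** **The plan's own figure.** The only power statement is above 90% for the composite (2500 people, 0.10 SD sustained, two-sided 0.05). Assume equal margins of 1250. The stated 5% yearly loss leaves on average 1250 × (0.95 + 0.95² + 0.95³)/3 = 1129 per margin. With an assumed equal correlation ρ between visits, the SD of mean change from baseline is √(4/3 × (1 − ρ)). At ρ = 0.60 this is 0.730 and power is 90.2%. So the figure is attainable, but it says nothing about the hazards model. There is no planned figure for MCI or dementia to reproduce.

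**Inputs for the hazards model**
- From the Protocol: "2500 participants from the parent trial who are at least 65 years of age"; 3 years of follow-up; 5% loss per year; two-sided 0.05. The last two are stated for the composite.
- Assumed: 1:1 at the margin; three-year control incidence 3–25%; conditional hazard ratio (HR) 0.70 or 0.80; one normally distributed baseline score whose log-hazard SD is 0.6 (moderate) or 1.0 (strong). Between people 1 SD above and 1 SD below the mean, these SDs mean hazard contrasts of exp(1.2) = 3.3-fold and exp(2.0) = 7.4-fold.

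**Method.** 1500 simulated trials per setting, exponential onset, Cox model fitted with treatment alone and with treatment plus the score. Monte Carlo error is about 1 point per power estimate.

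| Incidence | SD | True HR | Events | HR without / with score | Power without / with score | Gain (points) |
|---|---|---|---|---|---|---|
| 10% | 0.6 | 0.70 | 200 | 0.709 / 0.704 | 66.5% / 68.6% | 2.1 |
| 10% | 0.6 | 0.80 | 210 | 0.800 / 0.797 | 35.3% / 36.1% | 0.8 |
| 10% | 1.0 | 0.70 | 200 | 0.712 / 0.697 | 64.9% / 71.5% | 6.6 |
| 10% | 1.0 | 0.80 | 212 | 0.807 / 0.795 | 33.6% / 37.3% | 3.7 |
| 15% | 0.6 | 0.70 | 300 | 0.702 / 0.696 | 86.7% / 88.2% | 1.5 |
| 15% | 0.6 | 0.80 | 316 | 0.804 / 0.799 | 48.9% / 50.3% | 1.4 |
| 15% | 1.0 | 0.70 | 304 | 0.722 / 0.702 | 80.8% / 85.9% | 5.1 |
| 15% | 1.0 | 0.80 | 319 | 0.817 / 0.800 | 42.1% / 50.5% | 8.4 |

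**Hand check.** Power ≈ Φ(|ln HR|/SE − 1.96), for 10%, SD 1.0, HR 0.70:
- Without the score: |ln 0.7121|/0.1438 = 2.361, so Φ(0.401) = 65.6%.
- With the score: |ln 0.6970|/0.1439 = 2.509, so Φ(0.549) = 70.8%.

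Both agree with the simulation, and the standard errors are nearly equal. The gain therefore comes from the change in the hazard ratio.

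**Outside the central range.** At 3–6% incidence the gain runs from zero to 3.3 points (47.3% to 50.6%). At 25% it runs from 0.9 points to 12.1 (63.0% to 75.1%).

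**Annual detection.** A second simulation, with events found only at yearly visits, 600 trials per setting and HR 0.70, behaved the same way: 70% to 71% at SD 0.8 with 8% events, and 69% to 75% at SD 1.0 with 9% events.

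**Which covariate matters.** When the score was split at 10–15% incidence, an age-type covariate alone was worth about 0–2 points. Nearly all of the rest came from the baseline cognitive score when that was strong, for example 64% to 70%.

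**The case against.** A reader might infer that the plan has chosen an unadjusted model. The documents do not support that. The sentence neither names nor rules out covariates, and silence is a poor guide here: the SAP's paragraph on the primary analysis also lists none, although the Protocol specifies three. The covariate set is unspecified, so any power loss depends on a choice not yet recorded. This stands.

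A reader might also infer that a treatment-only model would be biased or would understate the truth. That does not follow either. Under randomization it estimates a marginal hazard ratio, which is a different quantity from the conditional one, and its test of no effect keeps its type 1 error. The gap between the two arises because hazard ratios are not collapsible, and has nothing to do with confounding. This stands too.

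The case for a strong predictor is only partly documented. The threshold of 31 is one of two triggers; the other is a fall of half a standard deviation against age norms in Years 1–3, which people with high entry scores can also meet. People below 31 at entry are screened then, and any classed as prevalent cases would leave the group at risk, narrowing its range. So the case-finding rule makes baseline TICSm a reasonable predictor without establishing an SD of 1.0.

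Finally, adding baseline TICSm goes beyond consistency with the primary model, and consistency alone buys little (about 0–2 points). That is fair, and it is why the recommendation names baseline TICSm.

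**Conclusion.** The point holds as a modest one about efficiency and pre-specification. The model for this secondary outcome names no covariates, and baseline cognition would be missing even if the primary model's covariates were carried over.

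Fitted with treatment alone, the analysis is valid but gives up some power. At 10–15% three-year incidence and a hazard ratio of 0.70–0.80, the loss is about 1–2 points with a moderate predictor and about 4–8 with a strong one. The hazard ratio moves by less than 0.01 in the first case and by about 0.01–0.02 in the second. With few events or weak predictors the loss is near zero.

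All these sizes rest on assumed incidence, effect and predictor strength, because the documents give none of them. The specification gap does not depend on those assumptions: as written, the covariates could be chosen after the results are seen. The primary analysis is unaffected.

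**What to change.** Replace the sentence in Protocol section 6, and put the same text in the SAP:

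> *Times to MCI and to dementia will be compared by proportional hazards regression adjusted for age, sex, education and baseline TICSm total, with the other factorial assignment in the model; the unadjusted hazard ratio will also be reported.*

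This needs no new data: age, sex and education are already in the primary model, and TICSm is part of the annual battery. The downside is that the main hazard ratio becomes conditional on the covariates. Reporting the unadjusted one beside it keeps the marginal estimate available. If the predictors prove weak, little is gained and little is lost.
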